#### 5.1.2. Matching external data

Due to the wide range of matching algorithms available and the difficulty in foreseeing all challenges upfront an additional operational step will be implemented as follows as part of the comparisons to external data:

An independent statistician will be identified. This statistician will be considered independent as they will have no knowledge or ability to access Part B later-onset post-baseline data in DEVOTE.

- The independent statistician will be provided with:232SM203 baseline covariates, baseline efficacy data and be unblinded to he assigned treatments. They will not have access to any on-treatment efficacy data for 232SM203Baseline data from CS4, Japan PMS, CS11.
- The following process will be followed:
- 1) The independent statistician will be provided with code to perform matching per this analysis plan and attempt to find the best match they can per the matching designs. In a situation where the matching approach is not successful then the statistician may implement an alternative matching algorithm.
- 2) If a match is found, then the independent statistician will create a dataset which identifies which groups of subjects were matched between studies.

Product: Nusinersen Study: 232SM203

3) Following the unblinding of 232SM203 the statistician responsible for the efficacy analysis will be provided with the file in (2) and perform the planned efficacy analysis using the groups of subjects identified. Since this statistician will have access to post-baseline efficacy data, they will not be permitted to perform the matching step (1,2).

This operational sequence is considered important in order to increase the chance of making a reasonable match, but also to protect the integrity of matching and minimize the bias which could occur if the statistician performing the matching had access to the efficacy data (or vice versa). Further details on this are described in the unblinding plan.

Product: Nusinersen	Statistical Analysis Plan
Study: 232SM203	Version: 1.0

#### Matching designs

1. Comparison of higher dose versus 12 mg nusinersen L3M6 dosing regimen

The intent is to match the 16 subjects in 232SM203 who received higher dose with a subset of subjects selected from the pool of subjects who received 12mg from baseline in: CS4, CS11 or the Japan PMS study. The matching design will follow the steps and number of subjects outlined in the following table:

Design	232SM203 higher dose	CS4 or CS11 or Japan PMS 12 mg

Product: Nusinersen		Statistical Analysis Plan
Study: 232SM203		Version: 1.0
1) Match 1 to 3	N= 16	N= 48
2) Match 1 to 2	N= 16	N= 32
3) Match 1 to 1	N= 16	N=16

#### 2. Higher dose versus 12 mg nusinersen from CS4 and CS11 controlled clinical trials L3M6 dosing regimen.

The matching design will be the same design as the design for comparison 2 but will use a smaller pool of patients as Japan PMS patients will not be included. In this analysis, baseline RULM will also be included as a covariate for matching

3. Matching design for comparison 4: higher dose versus CS4 Sham control

The matching design will be as shown in the table below. In this analysis baseline RULM will also be included as a covariate for matching

Design	232SM203 higher dose	CS4 Sham
1) Match 1 to 2	N= 16	N= 32
2) Match 1 to 1	N= 16	N= 16

# 5.1.4. Primary Efficacy Endpoints

#### N/A

# 5.1.5. Secondary Efficacy Endpoints

The following secondary efficacy endpoints will be evaluated for later-onset SMA population between 50/28 mg Group and 12/12 mg Group:

- Change from baseline in Hammersmith Functional Motor Scale Expanded (HFMSE) score
- Change from baseline in Revised Upper Limb Module (RULM) score
- Total number of new World Health Organization (WHO) motor milestones
- Change from baseline in neurofilament light chain (NfL) concentration in plasma
- Change from baseline in neurofilament light chain (NfL) concentration in CSF
- Change from baseline in Assessment of Caregiver Experience with Neuromuscular Disease (ACEND)
- Change from baseline in Pediatric Quality of Life InventoryTM (PedsQL)
- Number and duration of hospitalizations
- Clinical Global Impression of Change (CGIC) [physician, caregiver] at Day 302
- Number of serious respiratory events
- Ventilator use
- Change in the Parent Assessment of Swallowing Ability (PASA) scale

# Analysis Methods for HFMSE

The HFMSE is a tool used to assess motor function in children >2 years or older with later-onset SMA. The scale was originally developed with 20 scored activities and was devised for use in children with Type 2 and Type 3 SMA with limited ambulation to give objective information on motor ability and clinical progression. The expanded scale includes an additional module of 13 items developed to alleviate the ceiling effect and allow evaluation of higher functioning and ambulatory SMA patients. Each item is scored 0 (unable), 1 (performs with modification or adaption) or 2 (able) and the total score is calculated by summing the 33 items and ranges from 0 to 66 with higher scores indicating greater motor function. If 6 or fewer items are missing, then these items will be imputed to 0 when summing all 33 items. If greater than 6 items are missing, then the total score will be set to missing.

Baseline is defined as the last non-missing total score prior to the first dose of nusinersen.

In order to further explore the response as measured by HFMSE score a number of thresholds will be evaluated: The proportion of subjects achieving: worsening of >= 4, >= 3, >=2, >=1 points, any worsening, no change (=0 points), any improvement, >=1, >=2, >=3, >=4 points improvement will be presented.

Product: Nusinersen	Statistical Analysis Plan
Study: 232SM203	Version: 1.0

The main analysis is to compare the change from baseline HFMSE score at Day 302 between 50/28 mg Group and 12/12 mg Group using an ANCOVA model with treatment group as a factor and age at screening, baseline Plasma NfL and baseline HFMSE score as covariates. Missing post baseline HFMSE data will be handled using the multiple imputation method.

Several sensitivities will be performed for change from baseline HFMSE:

- The main analysis will be repeated using the PPS.
- The analysis will be performed using a Mixed Effect Model with Repeated Measures (MMRM) with an unstructured covariance matrix, where the treatment group, time (as a categorical variable), treatment by time interaction, and age at screening, baseline Plasma NfL, baseline HFMSE and baseline by time interaction will be included as covariates. No imputation for missing visit data will be performed and the analysis will be performed on the ITT set.
- The missing Day 302 values will be imputed by "last observation carried forward". This will be performed on the ITT set.
- Multiple imputation will be repeated, but for subjects who have a missing Day 302 assessment due to discontinuation for any reason, the worst of the subjects last observed value or the baseline value will be imputed. For subjects who completed but have a missing Day 302 value the imputed values will be used.

In order to further explore the change in HFMSE score during the study and the difference between treatment groups the change from baseline to each visit will be analyzed as described for the main analysis. A plot of mean change from baseline (based on the estimates from the ANCOVA model) over time will be provided by treatment group.

# Proportion of subjects achieving>=3 point improvement in HFMSE from baseline at Day 302:

The multiple imputation datasets produced for the main analysis will be utilized. If a subject terminates the study prior to Day 302 assessment, then the imputed value from the multiple imputation will be ignored and the subject will be considered a non-responder. Any subject in the ITT Set who has an increase from baseline HFMSE score of 3 or more points at Day 302 will be defined as a responder; otherwise, a subject will be considered a non-responder. Treatment groups will be compared using logistic regression adjusting for each subject's age at screening and baseline HFMSE.

If the logistic regression model does not converge then a Cochran–Mantel–Haenszel test will be performed instead.

#### Analysis Methods for RULM

The upper limb module test (Mazzone et al. 2011) was developed to assess the upper limb functional abilities in SMA patients using 9 items. However, a revised version of the upper limb module test developed by the Upper Limb Module Working Group will be performed in this

Product: Nusinersen	Statistical Analysis Plan
Study: 232SM203	Version: 1.0

study consisting of 20 items. The first item is assessed on a seven point scale ranging from 0 – "No useful function" to 6 – "Can abduct both arms simultaneously elbows in extension in a full circle until they touch above the head". This first item will not contribute to the total score. For the remaining 19 items, 18 items are assessed on a three point scale using the following criteria: 0 – Unable to achieve independently; 1 – Modified method but achieves goal independent of physical assistance from another person; 2 – Normal – achieves goal without any assistance. The one remaining item is assessed as either 0 or 1. For each item, a score will be collected on the left and right side. A derived total score will be calculated by summing the scores from these 19 individual items and ranges from 0 if the subject fails all activities to 37 if the subject achieves all activities. If, for an individual item, a response is recorded for both he left and right side the highest score will be used in calculating the total. If 3 or fewer items are still missing responses, then it will be assumed that the score was 0. If greater than 3 items are missing, then the total score will be set to be missing.

Baseline is defined as the last non-missing total score prior to the first dose of nusinersen.

In order to further explore the response as measured by upper limb score a number of thresholds will be evaluated: The proportion of participants achieving worsening of >= 4, >= 3, >=2, >=1 points, any worsening, no change, any improvement, >=1, >=2, >=3,>=4 points improvement will be presented.

The main analysis is to compare the change from baseline RULM total score at Day 302 between 50/28 mg Group and 12/12 mg Group using an ANCOVA model with treatment group as a factor and age at screening, baseline Plasma NfL and baseline RULM score as covariates. Missing post baseline RULM data will be handled using the multiple imputation method. Sensitivity analyses as described for the HFMSE will be performed.

#### Analysis Methods for Total Number of New WHO Motor Milestones

The WHO motor milestones are a set of six milestones in motor development, all of which would be expected to be attained by age 24 months in healthy children. The individual milestones are:

- Sitting without support
- Standing with assistance
- Hands and knees crawling
- Walking with assistance
- Standing alone
- Walking alone

Per the study inclusion criterion number 16, subjects would be expected to all have achieved and maintained at baseline the milestone "Sitting without support" but none would have achieved the milestone of "Walking alone". The motor milestones are assessed using the WHO motor milestone criteria [WHO Multicentre Growth Reference Study Group 2006]. As part of the

Product: Nusinersen	Statistical Analysis Plan
Study: 232SM203	Version: 1.0

assessment, the examiner records an overall rating of the subject's emotional state and then for each milestone one of the following four classifications:

- No (inability) Child tried but failed to perform the milestone
- No (refusal) Child refused to perform despite being calm and alert
- Yes Child was able to perform the milestone
- Unable to test Could not be tested because of irritability, drowsiness or sickness.

#### Imputation for motor milestones

If for a milestone either "No (refusal)" or "Unable to test" are observed at a visit, then the result will be first set to missing. Imputation will be performed for missing data considering each milestone separately using the following rules for scheduled visits.

For baseline, the closest non-missing milestone prior to or at first dose will be selected. If the motor milestone is still missing, then the missing value will be imputed as the median of the non-missing values of the stratum to which the subject belongs to: Age at screening <6 years or Age at screening >=6 years. In the event that the median at baseline is 0.5 then the missing value will be imputed as 1. If, for the subject with a missing value at a particular visit the corresponding visit is flanked by visits with non-missing milestones, the missing value will be imputed by using the worst result from the flanking visits. Otherwise, if the imputation is the last visit, the missing value will be imputed as the lowest value observed across all subjects who have a non-missing value at this visit within the stratum: Age at screening <6 years or Age at screening >=6 years within the treatment group. Of note, only observed data will be utilized for imputation purposes and in situation where unscheduled visit data is available these values will be utilized if these flank a missing visit. Missing motor milestone items will be imputed first prior to any analysis.

#### Main Analysis

The main analysis is to compare the total number of new motor milestones achieved at Day 302 between 50/28 mg Group and 12/12 mg Group, based on the ITT set. Missing data will be handled as described above and a total score for each visit calculated by summing the six milestones.

For each milestone the Day 302 and baseline values will be compared and if the subject can achieve a new milestone compared to baseline, then it will be counted +1, if the subject is unable to achieve the milestone, then it will be scored -1 and if the milestone has been maintained then it will be scored 0. These scores will then be summed to give a total score which could range between -6 (if a subject was able to perform all milestones at baseline but lost the ability and could not perform any milestones at Day 302) and +6 (if a subject was unable to achieve any milestones at baseline but could achieve all at Day 302).

The total number of new milestones achieved by each subject at Day 302 will be compared between treatment groups by ANCOVA with treatment group as the factor and subject age at screening, baseline Plasma NfL, and baseline number of milestones as covariates.

The following sensitivity analyses will be performed:

Product: Nusinersen	Statistical Analysis Plan
Study: 232SM203	Version: 1.0

- The main analysis will be repeated using the PPS.
- The analysis will be repeated in the ITT, with an exception to assign the worst of last available observation and zero (0) new motor milestones achieved for subjects who terminate the study prior to the Day 302 assessment.

#### Biomarker

The baseline for NfL is defined as the last non missing assessment prior to the first dose of study treatment. For Plasma NfL, if the baseline is missing and a NF-L result is available post dose at Day 1 or Day 2 than the first available assessment post dose, will be used as baseline.

Values that are BLQ will be set to half of the diluted LLOQ (34.5 pg/mL NfL in CSF and 2.76 pg/mL for NfL in plasma).

Neurofilament light chain (NfL) concentration in CSF and in plasma will be analyzed.

The baseline concentrations and the change (including absolute and ratio to baseline) will be presented by visit.

The analysis is to compare the adjusted mean change from (ratio to) baseline to Day 302 between 50/28 mg Group and 12/12 mg Group using an ANCOVA model with treatment group as a factor and age at screening, baseline CSF/Plasma NFL and baseline HFMSE score as covariates.

Summary tables and LS-mean plots (±SE) for geometric mean ratio to baseline in NfL in CSF/plasma using MI data +ANCOVA.

Spaghetti plots by visit for NfL in CSF/plasma using observed data will be plotted for all subjects.

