## 6.6. Analysis of the Remaining Secondary Endpoints - comparison: 50/28mg versus 12 mg Group from 232SM203

### 6.6.1. Change in CSF NF-L from (ratio to) baseline to Day 279

The analysis will be performed on the ITT set but is it noted that neurofilament CSF samples from China sites were not analyzed due to export law complication. The baseline and post baseline results for NF-L for these participants will be imputed in the MI step. Only baseline, Day 29 and Day 279 visits will be included as visits in the MI.

Values that are BLQ will be set to half of the diluted LLOQ (65 pg/mL).

The Neurofilament light chain (NF-L) CSF concentration change (including absolute and ratio to baseline) will be presented by visit.

Summary tables and LS-mean (+- 95% CI) plots for geometric mean ratio to baseline using MI data and ANCOVA will be presented.

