#### Secondary Endpoints

[figure not shown]
- Change from baseline in Hammersmith Functional Motor Scale Expanded (HFMSE) score.
- Change from baseline in Revised Upper Limb Module (RULM) score.
- Total number of new World Health Organization (WHO) motor milestones
- Change from baseline in neurofilament light chain (NfL) concentration in plasma.
- Change from baseline in neurofilament light chain (NfL) concentration in CSF.
- Change from baseline in Assessment of Caregiver Experience with Neuromuscular Disease (ACEND)
- Change from baseline in Pediatric Quality of Life InventoryTM (PedsQL)
- Number and duration of hospitalizations.
- Clinical Global Impression of Change (CGIC) [physician, caregiver] at Day 302
- Number of serious respiratory events
- Ventilator use
- Change in the Parent Assessment of Swallowing Ability (PASA) scale.

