# 2.1. Study Design

This 3-part study will evaluate the efficacy and safety of a higher dosing regimen of nusinersen in approximately 145 participants. The study will be conducted at approximately 65 sites globally. Following the completion of this study, all eligible participants may elect to enrol in a separate long-term extension study (232SM302), pending study approval by ethics committees and the appropriate regulatory authorities. In regard to participants rolling over from Part B, this will be done without unblinding the participant's treatment group.

Part B will consist of a pivotal, double-blind, active-controlled treatment period with either 2 or 4 loading doses of nusinersen (for the 50/28-mg Group and Control Group, respectively) administered intrathecally followed by maintenance doses approximately every 4 months thereafter. Approximately 75 participants with infantile-onset SMA and 24 participants with later-onset SMA will be randomized in a 1:2 ratio to receive either the currently approved dosing regimen or a 50/28-mg dosing regimen.

In the Control Group, up to a total of 8 participants will receive 4 loading doses of 12 mg of nusinersen administered intrathecally (Days 1, 15, 29, and 64), followed by maintenance doses of 12 mg on Days 183 and 279 (and a sham procedure on Day 135).

In the 50/28-mg Group, up to a total of 16 participants will receive 2 loading doses of 50 mg of nusinersen administered intrathecally (Days 1 and 15) and 2 sham procedures on Days 29 and 64, followed by maintenance doses of 28 mg on Days 135 and 279 (and a sham procedure on Day 183). In order to maintain blinding sham procedures will be used as shown in the table below.

Arm	Dose 1	Dose 2	Dose 3	Dose 4	Dose 5	Dose 6	Dose 7
50/28-mg	D1	D15	D29	D64	D135	D183	D279
Group	(50 mg)	(50 mg)	(sham)	(sham)	(28 mg)	(sham)	(28 mg)
Control (12/12	D1	D15	D29	D64	D135	D183	D279
mg)	(12 mg)	(12 mg)	(12 mg)	(12 mg)	(sham)	(12 mg)	(12 mg)
Group							

Randomization in Part B will be performed using interactive response technology (IRT).

Product: Nusinersen	Statistical Analysis Plan
Study: 232SM203	Version: 1.0

For Part B later-onset participants, the randomization will be stratified by age at informed consent as follows:

< 6 years and

 $\geq$  6 years

Blinded safety data will be reviewed on an ongoing basis by the Sponsor and the Medical Monitor. Unblinded safety data will be reviewed on an ongoing basis by an Independent Data Monitoring Committee (IDMC).

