#### 6.1.7. LP opening pressure

[figure not shown]
LP opening pressure will only be measured at Days 1, 15, and 279 to avoid potential unblinding. A lack of published data exists in terms of the variability of opening pressure between and within subjects. It is suspected that a simple change in position of a subject during the measurement or change of instrument used contributes to variability in the measurement.

[figure not shown]
The actual value and change from baseline to each visit will be summarized by treatment groups all the data collected will be listed.

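### Part B later-onset SAP: the between-arm CSF NfL analysis is set at Day 302, but the SAP's own schedule shows no lumbar puncture in either arm after Day 279

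*SAP*

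**What the plan says.** The later-onset SAP lists "Change from baseline in neurofilament light chain (NfL) concentration in CSF" among its secondary endpoints without naming a time point. The time point appears only in Section 5.1.5, under Biomarker. That text first says "Neurofilament light chain (NfL) concentration in CSF and in plasma will be analyzed", and then gives one analysis for both fluids: "The analysis is to compare the adjusted mean change from (ratio to) baseline to Day 302", with the 50/28 mg arm set against the 12/12 mg arm. The ANCOVA adjusts for "age at screening, baseline CSF/Plasma NFL and baseline HFMSE score as covariates", so the Day 302 sentence is meant to cover CSF as well as plasma. No other part of the later-onset SAP gives CSF a different day.

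Section 2.1 describes the 50/28 mg arm as having two 50 mg loading doses and shams on Days 29 and 64, "followed by maintenance doses of 28 mg on Days 135 and 279 (and a sham procedure on Day 183"). The control arm is dosed on Days 1, 15, 29, 64, 183 and 279, with a sham on Day 135. Neither arm has a dose or sham on Day 302. Section 6.1.6 names Day 302/ET separately from the dosing days. Section 6.1.7 states: "LP opening pressure will only be measured at Days 1, 15, and 279 to avoid potential unblinding".

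The infantile-onset SAP has the same dosing table. Its Section 6.6.1 is titled "Change in CSF NF-L from (ratio to) baseline to Day 279".

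**The concern.** CSF NfL can be measured only when CSF is collected, which in this trial happens at a lumbar puncture. If neither arm has a puncture at Day 302, the between-arm CSF comparison is defined at a visit where no sample is planned. The stated analysis could then not be run on observed data. Someone would have to choose another day at the analysis stage, possibly after unblinding, so the CSF comparison would lose its prespecified time point.

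The protocol does not obviously cover the gap. Section 12 of the later-onset SAP lists NfL as an endpoint added relative to the protocol-specified analyses, so the Biomarker paragraph is where its time point is fixed.

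**Working it through.** No power or error-rate figure is involved. The check sets the schedule beside the analysis time point.

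**Step 1. Real intrathecal procedures per arm (later-onset SAP, Section 2.1).**
- 50/28 mg arm: Days 1, 15, 135, 279 (shams on Days 29, 64, 183).
- 12/12 mg arm: Days 1, 15, 29, 64, 183, 279 (sham on Day 135).
- Days with a puncture in both arms: 1, 15 and 279. After baseline, that leaves Days 15 and 279.
- Day 302: none in either arm.

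**Step 2. Consistency with the rest of the SAP.**
- The study periods in Section 3.2 give 64 days of loading, 215 of maintenance and at least 23 of follow-up: 64 + 215 = 279, and 279 + 23 = 302. Day 302 therefore falls in follow-up, after the last dose.
- Section 6.1.6 does not count Day 302/ET as a dosing day.
- The opening-pressure days in Section 6.1.7 (1, 15, 279) are exactly the shared puncture days from Step 1.

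**Step 3. Can a Day 279 sample count as Day 302?** Section 4.4 applies windowing only to early-withdrawal and unscheduled assessments; scheduled visits keep their own label. For efficacy, the Day 302 window is ±14 days: 302 − 14 = 288 to 302 + 14 = 316. The gap is 302 − 279 = 23 days, which exceeds 14. The safety windows would not help either, since they assign Days 233 to 290 to the Day 279 visit.

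**Step 4. Planned observed CSF values at Day 302.** 0 of 16 in the 50/28 mg arm and 0 of 8 in the 12/12 mg arm, using the planned arm sizes.

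**Step 5. Can imputation fill the gap?** Section 5.1.1 applies multiple imputation to CSF NfL, using treatment, age, baseline values and all available post-baseline values. With no observed Day 302 CSF value in either arm, the Day 302 mean, variance and covariances with other visits cannot be estimated from the data. Imputation has nothing to draw on.

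**Step 6. Comparison with the infantile-onset SAP.** It sets CSF NF-L at Day 279 and gives plasma NF-L other days. Its summary of changes from Version 1.0 says a Day 64 CSF analysis was removed as not feasible because the 50/28 mg arm has a sham that day. The sponsor has therefore already applied this reasoning to the same dosing schedule.

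**The case against.** The strongest objection is that the key fact is inferred. The SAP never states when CSF is sampled in later-onset participants; that would normally be in the protocol's schedule of activities, which is not shown. Section 6.1.7 limits opening pressure, not CSF collection. This stands as a limit on certainty. A reader might infer that the documents prove 24 of 24 values missing by design. They do not: the zero count follows from the dosing table, and up to 4 further participants may be enrolled (Section 2.2). Still, every relevant section points the same way, and nothing in the SAP suggests a Day 302 CSF sample.

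A reader might also infer that the CSF endpoint is lost, or that a wholly imputed result would be reported. Neither follows. The Biomarker text also plans absolute change and ratio to baseline by visit, and spaghetti plots of observed data, so Day 279 CSF results would still appear. An imputation model with an empty visit would show its failure at once rather than quietly produce a number.

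Third, it is tempting to restrict all CSF displays to Days 1, 15 and 279. The SAP does not support that. No section shows that CSF NfL is measured on Day 15, and the restriction would drop legitimate single-arm observations (Day 135 in one arm; Days 29, 64 and 183 in the other). The infantile-onset SAP is no precedent for that list either: its CSF imputation uses baseline, Day 29 and Day 279, and Day 29 is a sham day for the 50/28 mg arm. It supports Day 279 as the endpoint and nothing more.

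Finally, the stakes are modest. The later-onset part has no primary efficacy endpoint, its sample size is not statistically based, and CSF NfL is one of 12 listed secondary efficacy endpoints. That stands and lowers the severity.

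**Conclusion.** The Day 302 time point is wrong as written for CSF NfL only. On the SAP's own schedule, the between-arm CSF ANCOVA has no planned observed data in either arm (0 of 16 and 0 of 8), the windowing rules do not allow Day 279 samples to stand in, and imputation cannot repair it. This is a stated rule that fails, not a detail left to the protocol. Plasma NfL at Day 302, the by-visit CSF summaries and the infantile-onset CSF analysis are unaffected.

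The conclusion assumes that CSF is collected only at the intrathecal procedures in the dosing table. A protocol sampling schedule with a Day 302 puncture would overturn it. The point should be fixed, but it concerns one secondary endpoint in a 24-participant exploratory comparison and does not threaten the trial's main result.

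**What to change.** Split the sentence in Section 5.1.5 into two: plasma NfL change (ratio) from baseline to Day 302, and CSF NfL change (ratio) from baseline to Day 279. Day 279 is the last day with a real lumbar puncture in both arms and the CSF time point in the infantile-onset SAP.

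State that the CSF imputation model and the between-arm LS-mean estimates use only visits at which CSF is sampled in both arms according to the protocol's sampling schedule, and name those visits once checked against it. Keep every observed CSF value, including single-arm days, in the descriptive summaries and spaghetti plots.

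The cost is SAP wording and the matching programming specification. No visit, procedure or sample changes.
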